### **Appendix 3: Guidelines for Everolimus and MMF/MPA dose reduction**

An investigator may interrupt temporarily or reduce, the dosage of study medication (Everolimus or MMF/MPA), if in his/her opinion this is clinically warranted, in response to any causally associated AE (e.g., neutropenia, thrombocytopenia, leukocytopenia, hyperlipidemia, hypertriglyceridemia or gastrointestinal intolerance). The following guidelines should be followed:

#### **1- PLATELETS**

Platelet count < 75,000/mm^3

Step 1: dose reduction should be considered and may be instituted at the discretion of the Investigator.

Step 2: if the platelet count remains below 75,000/mm^3 despite the initial dose reduction, a further dose reduction may be implemented per the table below:

Platelet count < 50,000/mm^3      Dose interruption should be considered.

Platelet count < 30,000/mm^3      Dose interruption will be mandatory.

If the platelet count returns to 30,000/mm^3 for 3 days, study medications may be restarted at lowest reduced dose. If the platelet count is stable at the reduced dose for 3 days, study medications may be increased to the next higher dose. If the platelet count remains stable at greater than 75,000/mm^3 for 7 days, the full dose of study medications may be restarted.

#### **2- WHITE BLOOD CELLS**

WBC < 3,000/mm^3 or absolute neutrophil count < 1,300/mm^3

Step 1: dose reduction should be considered and the first dose reduction may be instituted at the discretion of the Investigator.

Step 2: if the white count remains less than 3,000/mm^3 despite the intial dose reduction, a further dose reduction may be implemented per the table below:

If the WBC is less than 2,000/mm^3, dose interruption will be mandatory.

Once WBC returns to 2,000/mm^3 for 3 consecutive days, study medication may be restarted at the lowest level. If the WBC is stable at the reduced dose for 3 days, study medication may be increased to the next higher dose level. Once WBC returns to levels > 3,000/mm^3 for 7 days, study medication may be increased to the full dose.

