### **Arm 3 (MMF/MPA - Control group)**

Initial dosing of MMF/MPA will be 1000/720 mg BID (2/1.44 g/day) respectively for patients randomized into the MMF/MPA group. The dose should be adjusted for gastrointestinal intolerance and/or a decrease in WBC. For GI intolerance, the MMF/MPA dose should be reduced to 750 mg BID (1.5 g/day). If the GI intolerance persists, the dose can be reduced to 500 mg BID (1 g/day). MMF/MPA may be administered with antacids containing magnesium and aluminum hydroxides; however it is recommended that MMF/MPA and the antacid not be administered simultaneously. If neutropenia develops, dosing with MMF/MPA should be interrupted or reduced and the patient managed appropriately. The investigator is responsible for instructing the patients regarding the exact dose and dosing schedule to be followed.

MMF/MPA and TAC should be taken at the same time and consistently either before, during or after meals.

All dosages prescribed and dispensed to the patient and all dose changes during the study must be recorded on the Dosage Administration Record CRF.

The investigator should promote compliance by instructing the patient to take the study drug exactly as prescribed and by stating that compliance is necessary for the patient's safety and the validity of the study. The patient should be instructed to contact the investigator if he/she is unable for any reason to take the study drug as prescribed.

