## **Everolimus and MMF/MPA guidelines for dose reductions for safety reasons:**

For patients who are unable to tolerate the protocol-specified dosing schedule, dose adjustments are permitted in order to keep the patient on study drug. Reasons for study drug dose reductions may be for example, a decrease in the white blood cell count or platelet count, an increase in cholesterol or triglyceride level, gastrointestinal intolerance or other adverse events. Severe and unremitting changes may lead to study drug discontinuation. If study medication (ERL or MMF/MPA) is interrupted for safety reasons for 2 episodes of  $\geq 7$  consecutive days, or more than 21 consecutive days, discontinuation of study medication should be discussed with the sponsor.

During the course of the trial the study drugs will be administered on a BID regimen. Study medication will not be provided to patients after they have discontinued the study.

- Everolimus 1.5 mg treatment groups
  - It is recommended to reduce the dosing from the standard 0.75 mg BID to 0.5 mg BID. The dosing should, however, always follow a BID schedule.
- MMF/MPA 2,000/1,440 mg treatment group
  - MMF/MPA dose can be adjusted for gastrointestinal intolerance or a decrease in WBC. If neutropenia develops ( $ANC < 1,300/\text{mm}^3$ ) dosing with MMF/MPA should be interrupted or reduced, appropriate diagnostic tests performed and the patient managed according to local practice.

Additional information for dose adjustments based on laboratory values or other adverse events may be found in Appendix 3.

All changes in dosing of the investigational and control drug must be recorded on the Study Drug Dosage Administration Record CRF with date and reason.

The TAC dose must be adjusted to get  $C_{0-h}$  value within the pre-specified target range: for ERL Arm 1: 4 - 7 ng/mL from Day 1 until Month 3, and 2 - 5 ng/mL starting at the Month 3 Visit; for ERL Arm 2: 4 – 7 ng/mL from Day 1 until Month 3, where the patient will be converted from TAC to MMF/MPA; for SOC arm 3: 8 - 12 ng/mL starting at Day 1 until

Month 12, and 6 – 8 ng/mL from Month 12 until study completion. If TAC is held for > 14 days, study drug should be discontinued and the patient discontinued from the study.

These changes must be recorded on the Dosage Administration Record CRF.

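### Appendix 3 lets MMF/MPA return to full dose on the white count alone, even while the neutrophil count is below the 1,300/mm³ at which section 6.5.5 says to interrupt or reduce

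*Combined protocol and SAP*

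**What the plan says.** Appendix 3, part 2 (white blood cells), opens with two alternative triggers: WBC below 3,000/mm³, "or absolute neutrophil count < 1,300/mm"³. Five rules follow:

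- Further reduction applies "if the white count remains less than 3,000/mm"³.
- Interruption is mandatory when WBC is below 2,000/mm³.
- Restart at the lowest level is allowed after WBC has been back at 2,000/mm³ for 3 consecutive days.
- Step-up: "If the WBC is stable at the reduced dose for 3 days, study medication may be increased to the next higher dose level".
- Full dose: with WBC above 3,000/mm³ "for 7 days, study medication may be increased to the full dose".

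Section 6.5.5 (dose reductions for safety reasons) has its own rule for the MMF/MPA group. At ANC below 1,300/mm³, "dosing with MMF/MPA should be interrupted or reduced, appropriate diagnostic tests performed". Section 6.5.4 (Arm 3) says, without a threshold: "If neutropenia develops, dosing with MMF/MPA should be interrupted or reduced and the patient managed appropriately". Section 6.5.5 presents Appendix 3 as a source of additional information on laboratory-based adjustment. Neither place says which rule prevails if they differ.

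**The concern.** A low ANC can start the dose reduction, but it plays no part in ending it. A clinician who works down the Appendix 3 list could put a patient back on full-dose MMF/MPA while the neutropenia that called for a lower dose persists, and could cite the protocol for doing so. At the same blood count, section 6.5.5 points the other way with a stronger verb. Nothing else in the documents supplies an ANC recovery criterion. What is at stake is patient safety and consistent dosing between patients. No error rate or estimate is affected.

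**Working it through.** No sample-size or power figure is involved. The check is to read the rules literally and find the blood counts at which they disagree.

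**Inputs.** Entry trigger: WBC < 3,000 or ANC < 1,300 (Appendix 3, part 2). Full-dose condition: WBC > 3,000 for 7 days (same place). MMF/MPA interrupt-or-reduce condition: ANC < 1,300 (section 6.5.5). Planned arm size: 16 (section 6.3). All counts are per mm³.

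**Step 1: where ANC appears.** Of the five Appendix 3 rules after the entry line, the number that mention ANC is 0.

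**Step 2: which counts satisfy both conditions.** ANC = WBC × neutrophil fraction, so ANC is below 1,300 when the fraction is below 1,300 / WBC.

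| WBC, held for 7 days | Fraction below which ANC < 1,300 |
|---|---|
| just above 3,000 | 1,300 / 3,000 = 43.3% |
| 3,500 | 1,300 / 3,500 = 37.1% |
| 4,000 | 1,300 / 4,000 = 32.5% |

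The WBC values are illustrative; the documents give no distribution of counts.

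**Step 3: one patient under each rule.** Take WBC 3,500 for 7 days with ANC 1,200, a neutrophil share of 1,200 / 3,500 = 34.3%.

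| Rule | Result |
|---|---|
| Appendix 3, full dose (WBC > 3,000 for 7 days) | met: full dose permitted |
| Appendix 3, entry trigger (ANC < 1,300) | still met: reduction to be considered |
| Section 6.5.5, MMF/MPA (ANC < 1,300) | met: interrupt or reduce |

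**Step 4: the 3-day step-up.** This rule asks only for a stable WBC. If the next level up is the full dose, it reaches full dose without the 7-day condition. Section 6.5.4 names 750 mg and 500 mg BID as reduced MMF/MPA doses for gastrointestinal intolerance. If those levels also serve for cytopenia, a patient on 750 mg BID is one step from 1,000 mg BID. The dose table that Appendix 3 points to is not in the text available here, so this stays conditional.

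**Step 5: reach.** The section 6.5.5 rule is listed under the 2,000/1,440 mg MMF/MPA group, and the section 6.5.4 sentence is for Arm 3. The clear reach is 16 planned patients. If the rule also covers Arm 2 after its Month 3 conversion, it is 16 + 16 = 32 of 48.

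**The case against.** The strongest reply is that a clinician can obey both texts. Appendix 3 says full dose *may* be given; section 6.5.5 says MMF/MPA *should* be interrupted or reduced; declining an optional increase breaches neither. Section 4 also leaves MMF/MPA adjustment for side effects to institutional practice, and Appendix 3 opens by relying on the investigator's judgement and names neutropenia as an example. This stands as a reason for low severity. It does not remove the disagreement, because the protocol still authorises an increase at a count where it elsewhere advises the opposite.

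A second reply is that the full-dose sentence speaks of WBC returning above 3,000/mm³, so it presupposes that WBC had fallen. On that reading, a patient who entered on ANC alone is not covered, and the tension is confined to patients whose WBC fell and recovered while ANC stayed low. That is a fair reading. It narrows the conflict but leaves the ANC-only patient with no return rule in Appendix 3.

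A reader might also infer more than the documents support:

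- *A parallel platelet conflict.* Appendix 3 says "If the platelet count is stable at the reduced dose for 3 days, study medications may be increased to the next higher dose", which could apply between 30,000 and 50,000/mm³, where the same list says "Dose interruption should be considered". Considering interruption forbids nothing, so a cautious increase in a stable patient is compatible with it. A floor of 50,000/mm³ would be a clinical choice.
- *An ANC condition on every step-up.* An intermediate dose that is still reduced already satisfies section 6.5.5.

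**Conclusion.** The inconsistency is real and minor. The full-dose rule in Appendix 3 omits one of its own two entry criteria and so permits full-dose MMF/MPA at ANC below 1,300/mm³, against section 6.5.5. The clear reach is Arm 3, 16 planned patients; a reader might take it as 32 of 48, but that depends on extending the section 6.5.5 rule to Arm 2. Either figure is the number of patients to whom the rule could apply, not a number harmed.

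The conclusion assumes that the dose table Appendix 3 refers to contains no ANC return criterion. The protocol's list of tables shows no such table, which makes this likely but does not prove it. The conflict is specific to MMF/MPA, since section 6.5.5 gives no ANC rule for everolimus.

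**What to change.** Amend the full-dose sentence in Appendix 3, part 2, to require WBC above 3,000/mm³ and ANC of at least 1,300/mm³, both sustained for 7 days, before study medication goes back to full dose. Add one sentence saying that this condition governs any return to full dose, including by the 3-day step-up. The 1,300/mm³ figure is the existing entry threshold, so no new cut-off is introduced. Restart at the lowest level, intermediate reduced-dose steps and the platelet rules stay as they are.

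The cost is amendment wording. Section 7.5.7 already puts ANC on the same hematology panel as WBC. Scheduled counts are a month or more apart from Month 2 on, so confirming 7 days may need an unscheduled repeat count, as the existing WBC condition already can.

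The clinical price is that some patients stay on a reduced dose longer, with somewhat less immunosuppression in a trial whose primary endpoint includes treated BPAR. Because the Appendix 3 rules cover both study drugs, a held-down everolimus dose could also leave the trough at or below 3 ng/mL, which section 6.5.8 lists as a reason to discontinue if the level cannot be maintained.

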#### **3- CHOLESTEROL**

If cholesterol and/or triglycerides are found to be elevated, dosing should be reconsidered and optimized as appropriate, in addition to provided dietary advice. If the elevation is confirmed by a second measurement within 2 weeks under fasting conditions (last meal  $\geq$  8 hours prior to sampling) the following guidelines are recommended.

Cholesterol  $>$  250 - 450 mg/dL or  $>$  6.5 - 11.6 mmol/L:

Dietary instruction is strongly recommended and statin therapy, e.g. fluvastatin, should be considered (see Appendix 4)

**If the abnormality persists, the dosing of study medication will be adjusted as follows:**

Cholesterol  $\geq$  450 mg/dL or 11.6 mmol/L: Dose reduction should be considered

Cholesterol  $>$  750 mg/dL or  $>$  19.4 mmol/L: Study medication should be interrupted

#### **4- TRIGLYCERIDES**

Triglycerides  $>$  250 mg/dL or  $>$  2.9 mmol/L:

Dietary instruction is strongly recommended and statin therapy should be considered

**If the abnormality persists, the dosing of study medication will be adjusted as follows:**

Triglycerides  $\geq$  600 mg/dL or  $\geq$  6.9 mmol/L: Dose reduction should be considered

Triglycerides  $>$  1000 mg/dL or 11.4 mmol/L: Study medication should be interrupted

**Table 13-2 National cholesterol education program guidelines**

#### **Total cholesterol**

Under 200 mg/dL	Desirable
200-239 mg/dL	Borderline-high
240 and over	High

#### **HDL cholesterol**

Under 35 mg/dL	Low
----------------	-----

Table 13-3 Treatment based on LDL cholesterol

Diet therapy	Initiation level	LDL goal
Without CHD and without 2 risk factors	160 mg/dL or over	Under 160 mg/dL
Without CHD and with 2 or more risk factors	Over 130 mg/dL	Under 130 mg/dL
With CHD	Over 100 mg/dL	100 mg/dL or under
Drug treatment	Initiation level	LDL goal
Without CHD and without 2 risk factors	190 mg/dL or over	Under 160 mg/dL
Without CHD and with 2 or more risk factors	160 mg/dL or over	Under 130 mg/dL
With CHD	130 mg/dL or over	100 mg/dL or under

(Data from Expert Panel on Detection, Evaluation and Treatment of High Blood Cholesterol in Adults: Summary of the second report of the National Cholesterol in Adults [Adult Treatment Panel II] JAMA 269[23]:3015-3023, 1993)

#### Appendix 4: Possible Everolimus drug-drug interactions

During treatment with immunosuppressive agents, such as everolimus, steroids and tacrolimus, vaccination may be less effective. The use of live vaccines should be avoided.

Table 13-4 Everolimus Drug Interactions

Drugs not allowed	Sirolimus	Patients to be discontinued from everolimus if given
	Terfenadine Astemizole Cisapride	Inhibitors of P-450 (CYP), in particular CYP3A (as everolimus) have the potential to increase the exposure of these drugs resulting in prolongation of QT intervals on

ECGs		
	Ketoconazole* Clarithromycin Telithromycin Ritonavir	Strong inhibitors of P-450 (CYP) have the potential to increase the exposure of everolimus
	Rifampicin Rifabutin	Strong inducers of P-450 (CYP) have the potential to decrease the exposure of everolimus
Drugs strongly discouraged	Lovastatin** Simvastatin**	Confirmed interaction between everolimus and this drug
	Cerivastatin** Rosuvastatin**	Insufficient data available to make recommendations regarding concomitant use of the newer statins and everolimus
	Quinidine Fluoxetine Paroxetine	Potential interaction of everolimus with CYP 2D6 substrates
	Itraconazole* Voriconazole*	Strong inhibitors of P-450 (CYP) have the potential to increase the exposure of everolimus
Drugs necessitating close monitoring	Digoxin	Potential interaction with everolimus has not been evaluated, patients on digoxin should have periodic measurements of digoxin levels
	Fluconazole*	Strong inhibitors of P-450 (CYP) have the potential to increase the exposure of everolimus

\* The concomitant administration of the antifungal agent ketoconazole, is prohibited in patients who are taking everolimus. If ketoconazole must be administered, everolimus must be discontinued. If -azole antifungal agents must be administered to patients, everolimus blood levels must be monitored closely. The investigator should anticipate the need to reduce or withhold the dose of everolimus. Fluconazole may pose the smallest risk for drug-drug interactions.

\*\* Patients requiring treatment with this class of medication (especially lovastatin) should be monitored closely for signs of rhabdomyolysis, such as dark-colored urine, fever, muscle cramps, pain, spasm, or stiffness, unusual tiredness or weakness.

## Appendix 5: Possible tacrolimus drug-drug interactions

Due to the potential for additive or synergistic impairment of renal function, care should be taken when administering tacrolimus with drugs that may be associated with renal

dysfunction. These include, but are not limited to: aminoglycosides, amphotericin B and cisplatin. Since tacrolimus is metabolized mainly by the CYP3A enzyme systems, substances known to inhibit these enzymes may decrease the metabolism of tacrolimus with resultant increases in whole blood or plasma concentrations. Drugs known to induce these enzyme systems may result in an increased metabolism of tacrolimus and decreased whole blood or plasma concentrations. Monitoring of blood concentrations and appropriate dosage adjustments are essential when such drugs are used concomitantly.

Table 13-5 **Drugs that may affect Tacrolimus blood concentrations**

Calcium channel blockers	Antifungal agents	Gastrointestinal prokinetic agents
Diltiazem	Clotrimazole	Cisapride
Nicardipine	Ketoconazole	Metoclopramide
Nifedipine	Fluconazole	
Verapamil	Itraconazole	
Macrolide antibiotics	Other drugs	
Clarithromycin	Bromocriptine	
Erythromycin	Cimetidine	
Troleandomycin	Cyclosporine	
	Danazol	
	Methylprednisolone	
	Protease inhibitors	
Drugs that may decrease tacrolimus blood concentrations		
Anticonvulsants	Antibiotics	
Carbamazepine	Rifabutin	
Phenobarbital	Rifampin	
Phenytoin		

Interaction studies with drugs used in HIV therapy have not been conducted. However, care should be exercised when drugs that are nephrotoxic (e.g., ganciclovir) or that are metabolized by CYP3A (e.g., ritonavir) are administered concomitantly with tacrolimus. Grapefruit juice affects CYP3A-mediated metabolism and should be avoided.

Immunosuppressants may affect vaccination. Therefore, during treatment with tacrolimus, vaccination may be less effective. The use of live vaccines should be avoided.

## **Appendix 6: Possible MMF/MPA drug-drug interactions**

The use of live attenuated vaccines should be avoided and patients should be advised that vaccinations may be less effective. Influenza vaccinations may be of value.

Table 13-6 Possible MMF/MPA Drug-Drug Interaction

Drugs not allowed	Cholestyramine	Patients to be discontinued from CellCept, if given
Drugs strongly discouraged or not to be administered simultaneously	Acyclovir or prodrug-Valacyclovir	Competition for tubular secretion may increase the concentration of CellCept
	Sevelamer CA 2+ free phosphate binders	CA 2+ free phosphate binders to be given 2 hours after CellCept to minimize impact on absorption
	Norfloxin together with Metronidazole	Not recommended to be given concomitantly with the combination of both drugs
	Antacids with magnesium and aluminum hydroxides	Do not take simultaneously, administer alone under fasting conditions
Drugs necessitating close monitoring	Ganciclovir or prodrug-Valganciclovir	Competition for tubular secretion may increase the concentration of CellCept
